8.1 Definitions

8.1.1 Adverse Event (AE)

An adverse event (AE) is defined as any untoward medical occurrence, unintended disease or injury, or untoward clinical signs (including abnormal laboratory findings) in subjects, users or other persons, whether related to the investigational medical device or procedure.

8.1.2 Adverse device effect (ADE)

An adverse device effect is defined as an adverse event related to the use of an investigational medical device. This includes any adverse event resulting from insufficiencies or inadequacies in the instructions for use, the deployment, the implantation, the installation, the operation, or any malfunction of the investigational medical device. This definition includes any event resulting from use error or from intentional misuse of the investigational medical device.

8.1.3 Serious Adverse Event (SAE)

A serious adverse event (SAE) is defined as any adverse event that

- led to death
- led to serious deterioration in the health of the subject, that either resulted in
 - 1) a life-threatening illness or injury, or
 - 2) a permanent impairment of a body structure or a body function, or
 - 3) in-patient or prolonged hospitalization, or
 - 4) medical or surgical intervention to prevent life-threatening illness or injury or permanent impairment to a body structure or a body function,
- led to fetal distress, fetal death or a congenital abnormality or birth defect

NOTE Planned hospitalization for a pre-existing condition, or a procedure required by the CIP, without serious deterioration in health, is not considered a serious adverse event.

8.1.4 Serious adverse device effect (SADE)

8.1.5 A serious adverse device effect is defined as an adverse device effect that has resulted in any of the consequences characteristic of a serious adverse event. Unanticipated Adverse Device Effects

8.1.6 Unanticipated adverse device effects refer to any event that represents a “serious adverse effect on health or safety or any life-threatening problem or death caused by, or associated with, a device if that effect, problem or death was not previously identified in nature, severity, or degree of incidence in the investigational plan or application, or any other unanticipated serious problem associated with a device that relates to the rights, safety, or welfare of subjects.” [FDA 21 CFR 812.3(s)] Device deficiency (DD)

A device deficiency is defined as an inadequacy of a medical device with respect to its identity, quality, durability, reliability, safety or performance. Device deficiencies include malfunctions, use errors, and inadequate labelling. For the purposes of this study, the device of study is the AI software and related functions to complete testing and/or programming.

8.2 Assessment and Reporting of Adverse Events and device deficiencies

To monitor subject safety throughout this study, device deficiencies and device and/or procedure-related serious adverse events will be recorded. Information on these adverse events will be maintained by event type. The investigator will complete an Adverse Event and/or Device Deficiency form.

In accordance with 21 CFR 812.3, Investigators are required to inform their respective Institutional Review Boards (IRBs) and Cochlear Americas immediately if an unanticipated adverse device effect is suspected (no more than 10 working days after the investigator learns of the effect). If the case is determined to be an unanticipated adverse device effect, the investigator will fill out an “Unanticipated Adverse Device Effect Form.” Cochlear Americas will report the results of an evaluation of the unanticipated adverse device effect to the FDA and all other reviewing IRBs and investigators within 10 working days after first receiving notice of the event.

The investigator shall report all serious device and procedure related adverse events and device deficiencies that could have led to a serious adverse event to the sponsor and respective IRBs per local requirements.

The Sponsor will report adverse event and device deficiency information to the respective IRBs per local requirements.

The details of the Medical Monitor responsible for the clinical investigation are:

Name of contact person of the sponsor	[REDACTED]
Phone number (business hours)	[REDACTED]
Phone number (after hours)	[REDACTED]
E-mail	[REDACTED]

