11.2 Risks

With any cochlear implant mapping, there is a very small risk of unintentional over-stimulation. Subjects may experience sounds during mapping that are uncomfortably loud. Mitigation of this risk is similar to that used during clinical cochlear implant mapping wherein the sound processor is removed from the subjects' head and/or the stimulation to the sound processor is ceased in Custom

Sound. This is a modified clinical treatment plan and therefore the possibility of patient dissatisfaction and reduced performance.

12. Good Clinical Practices Statement

The study obligations for the Investigator(s) are outlined in guidelines for Good Clinical Practice (GCP), 21 CFR Part 812 (Code of Federal Regulations Part 812 Investigational Device Exemptions), ISO14155:2011 (Clinical Investigation of Medical Devices for Human Subjects – Good Clinical Practice), and the Declaration of Helsinki.

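### Section 8.2 limits adverse event recording to related serious events, which conflicts with Tables 1 and 2 and leaves the named over-stimulation risk without a required, comparable record in both groups

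*Protocol*

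**What the plan says.** Section 8.2 sets the rule for what is collected: "device deficiencies and device and/or procedure-related serious adverse events will be recorded". The reporting duty later in the same section has a similar limit: "The investigator shall report all serious device and procedure related adverse events and device deficiencies that could have led to a serious adverse event".

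The definitions in section 8.1 are wider. An adverse event is "any untoward medical occurrence, unintended disease or injury, or untoward clinical signs", and section 8.1.2 adds: "An adverse device effect is defined as an adverse event related to the use of an investigational medical device". Neither carries a seriousness threshold. The threshold comes in section 8.1.3, with criteria such as "a permanent impairment of a body structure or a body function".

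Tables 1 and 2 in section 7 each carry a row for adverse events and device deficiencies, marked at switch-on and at 1, 3 and 6 months in both groups, and also at 1-2 weeks in Group B. Neither row is restricted to serious or related events. Section 10.2 defines the intention-to-treat set for adverse event reporting, and section 10.3 puts the occurrence of adverse events among the priorities for follow-up, again without that limit.

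Section 11.2 says that with any mapping "there is a very small risk of unintentional over-stimulation" and that "Subjects may experience sounds during mapping that are uncomfortably loud". It also mentions "the possibility of patient dissatisfaction and reduced performance".

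**The concern.** The recording rule and the visit schedule give a site two different instructions. With up to 5 sites, one that works from section 8.2 will leave non-serious events unrecorded, and one that works from the tables may record them. The pooled adverse event data would then depend on which section each site followed.

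The gap falls on the harm that the protocol itself warns of. Group A goes home on AI-created maps and is managed with less clinical time, and section 4 sets the goal of doing this without loss of outcomes or satisfaction. Whether such maps are tolerated as well as conventionally made ones is a natural safety comparison. It needs the same events to be collected by the same rule in both groups. Later analysis cannot repair this, because events that were not recorded cannot be analysed.

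**Working it through.** No arithmetic applies. The point concerns the scope of recording and depends on no rate, sample size or error level. The check sets the sections side by side.

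1. **Does section 8.2 govern recording, or only expedited reporting?** The sentence quoted from it says what is recorded for safety monitoring, and the investigator's reporting duty follows separately. No sentence in section 8.2 requires a record of a non-serious adverse event, related or not.

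2. **Is the named risk serious under the protocol's own definition?** Section 8.1.3 lists death, life-threatening illness or injury, permanent impairment, hospitalization, intervention to prevent life-threatening or permanent harm, and fetal harm. Section 11.2 describes uncomfortable loudness, handled by taking the processor off or stopping stimulation. As described, it meets none of these criteria. This is an inference, since the protocol does not itself classify the event.

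3. **Do other sections carry the same limit?** No. The adverse event rows in Tables 1 and 2 and the wording of sections 10.2 and 10.3 refer to adverse events in general.

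4. **Does the device deficiency route fill the gap?** Only in part. Deficiencies are recorded at any severity and include malfunctions and use errors. However, the definition at the end of section 8.1 names the AI software and its testing and programming functions as the device of study. Group B is programmed as each centre defines, so a loud episode at a Group B mapping session has no matching route.

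5. **Do other forms fill it?** Only in part:
   - The Unscheduled Visit Form (section 5.3.1.4) records the reason for interim visits in both groups.
   - The Communication Documentation form (section 5.3.1.5) records contacts from the subject in both groups.
   - Loudness scaling (section 5.3.1) includes a rating for too loud, but it is a fitting test in Group A only.

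   None of these requires a record of over-stimulation that begins and ends within a scheduled mapping session.

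6. **Are the other risks in section 11.2 covered?** Yes. Dissatisfaction and reduced performance are measured in both groups by the satisfaction survey, SSQ-12 and CNC words. Over-stimulation has no equivalent measure across both groups.

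**The case against.** The strongest reply is that this is a wording mismatch, not a blind spot. Section 8.2 also records device deficiencies, so a loud AI map judged to be a malfunction, a use error or a safety inadequacy can be logged in Group A, which is the group of most interest. The tables may lead some sites to record non-serious events anyway. Interim visits and subject contacts are documented in both groups. The protocol calls the risk very small and describes its mitigation as similar to that in ordinary clinical mapping. A definition that is wider than the recording rule is not in itself a contradiction.

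Much of this stands, and it rules out two stronger readings:

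- **That the study cannot detect over-stimulation at all, or that its recorded count must be zero.** A reader might infer this from section 8.2 alone. The documents do not support it: the sections conflict, so capture is uncertain rather than absent, and partial routes exist. Nor can an expected number of missed events be calculated, because the protocol gives no rate.
- **That the schedule biases the comparison, because adverse events are marked at 4 post-activation points in Group A and 5 in Group B.** The extra Group B mark belongs to a clinic visit at which programming may take place. The Group A video call is counselling on equipment, with no mapping listed, and the named risk arises during mapping. The difference in marks follows from the care schedules that the trial compares.

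The reply does not remove the conflict between section 8.2 and the tables. Nor does it supply a required record, on equal terms in both groups, of an over-stimulation episode within a mapping session.

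**Conclusion.** The point holds as a conflict over what is collected. Section 8.2 confines adverse event recording to related serious events, while Tables 1 and 2 and sections 10.2 and 10.3 do not. Under section 8.2 the protocol's one named physical risk has no required adverse event record, and the route that partly covers it is in practice open to Group A only. Capture is therefore neither reliable across sites nor comparable between groups.

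The size is qualitative: it affects which safety data exist, not the primary endpoint of appointment minutes. The conclusion rests on two assumptions: that uncomfortable loudness at mapping counts as an adverse event under the broad definition in section 8.1.1, and that it is non-serious as section 11.2 describes it. The protocol states neither outright. The change should be made, since it is specific and cheap.

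**What to change.** Amend section 8.2 so that it agrees with the adverse event rows in Tables 1 and 2. Require that all device-, software- and procedure-related adverse events, serious or not, be recorded on the existing Adverse Event form in both groups. Name over-stimulation or uncomfortable loudness at mapping as an event to record, whether the map came from the AI tool or from the centre's usual programming, so that Group B events are not lost through the definition of the device of study. Leave the expedited reporting rules for serious events and unanticipated device effects unchanged. Check that sections 10.2 and 10.3 then refer to the same set of events.

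The cost is amendment wording, a short instruction to sites and a few more Adverse Event forms per site. An added adverse event entry at the Group A video call is optional and is not needed to resolve this point.

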5.5.3 One Month Post activation

At 1-month post activation, the following procedures will be completed:

- New Model (Group A)
 - Confirm Device use through usage data screen in Custom Sound
 - Optional: AutoNRT if not collected in the OR at the time of surgery
 - Evaluate highest tolerable AutoMAP

- Administer psychoacoustic tests using direct connect:
 - Complete Audiogram – obtain FOX (AI) advice
 - Complete phoneme discrimination and obtain FOX (AI) advice
 - Provide AI MAP to subject for take home use
- Complete Rehabilitation Screener and provide list of resources
- Provide appropriate accessory materials for self-driven learning based on goals of COSI and ability of subject
- Communication documentation form
- An anonymized .cdx file will be provided to the study sponsor
- Traditional Model (Group B)
 - Programming and/or counselling as defined by Center
 - Communication documentation form
 - An anonymized. cdx file will be provided to the study sponsor

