10.3 Missing Data

All efforts will be put forth to ensure near complete follow-up, with focus on the assessment of the primary outcome and occurrence of adverse events. Regular reminders of subject follow-up due dates will be provided to participating centers to facilitate scheduling of follow-up visits.

11. Risk Benefit Statement

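### Section 8.2 records only serious related adverse events, while the visit tables and sections 10.2 and 10.3 set no such limit, so non-serious over-stimulation lacks one recording rule common to both arms

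*Protocol*

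**What the plan says.** Section 8.2 sets the recording rule: "device deficiencies and device and/or procedure-related serious adverse events will be recorded". Investigator reporting is limited in a similar way: "The investigator shall report all serious device and procedure related adverse events and device deficiencies that could have led to a serious adverse event". The instrument is named without a seriousness limit: "The investigator will complete an Adverse Event and/or Device Deficiency form".

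Under section 8.1.3 an event is serious if it caused death or a fetal or congenital outcome, or if it "led to serious deterioration in the health of the subject, that either resulted in" life-threatening illness, permanent impairment, hospitalisation, or an intervention to prevent such outcomes.

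The device deficiency definition at the end of section 8.1 adds: "For the purposes of this study, the device of study is the AI software and related functions". The sentence goes on to cover functions used for testing or programming.

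Section 11.2 attaches a risk of unintentional over-stimulation to any cochlear implant mapping and describes how it presents: "Subjects may experience sounds during mapping that are uncomfortably loud".

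Other passages are wider than 8.2:

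- Sections 8.1.1 and 8.1.2 define adverse events and adverse device effects with no seriousness threshold.
- Tables 1 and 2 carry a row for adverse events and device deficiencies at each post-activation clinic visit.
- Section 10.2 makes all consented subjects the population for adverse event reporting.
- Section 10.3 promises near-complete follow-up "with focus on the assessment of the primary outcome and occurrence of adverse events".

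**The concern.** The protocol names one physical risk of the study procedures, and the section that tells sites what to record does not clearly reach it. Sound that is uncomfortably loud and stops when the processor is removed or stimulation ceases would ordinarily meet no criterion in 8.1.3. The remaining route in 8.2, device deficiency, is tied to a device that is part of the Group A intervention.

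Two things are at stake. First, sites may differ: up to 5 centers could read the scope from 8.2 or from the tables and return different data on the same kind of event. Second, arms may differ: the deficiency route is open, conditionally, in Group A and has no clear counterpart in Group B. Group A's way of setting stimulation differs from usual care, with AutoMAPs, an instruction at one month to "Evaluate highest tolerable AutoMAP", and AI MAPs for take-home use. A fair comparison of this risk between the models is therefore worth having, given the stated aim in section 4 of saving time without loss of outcome or satisfaction. An analysis plan cannot recover events that sites were told not to record.

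**Working it through.** No arithmetic applies. The check takes a single non-serious over-stimulation event and asks which provision would capture it in each arm.

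| Provision | Group A | Group B |
|---|---|---|
| 8.2, serious related adverse event | No: ordinarily meets no criterion in 8.1.3 | No: same reason |
| 8.2, unanticipated adverse device effect | No: the definition requires a serious effect or problem | No: same reason |
| 8.2, device deficiency | Only if judged an inadequacy (such as malfunction, use error or labelling) of the AI software or related functions | No clear route: 5.5.1 to 5.5.5 leave programming to the center and list no AI step. Open only if related functions include ordinary programming software |
| Tables 1 and 2 with 8.1.1 | Can be recorded at switch-on, 1, 3 and 6 months | Can be recorded at switch-on, 1-2 weeks, 1, 3 and 6 months |
| 5.3.1.4, Unscheduled Visit Form | Only if an interim visit takes place | Same |
| 5.3.1.5, Communication Documentation form | Only if the subject contacts the clinic or manufacturer | Same |

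Four steps follow.

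1. The first three rows are what 8.2 provides. Together they give no certain capture in either arm, and the one conditional route is not equal between arms.
2. The fourth row gives capture in both arms. It conflicts with the first, because 8.2 restricts what is recorded to serious related events and the tables do not.
3. Sections 10.2 and 10.3 agree with the tables. Within 8.2, the form's name and the sentence on sponsor reporting to the IRBs also lack a seriousness limit. The conflict therefore runs partly inside 8.2 itself.
4. The last two rows are incidental. They miss an event that begins and ends within a mapping session, which is the setting 11.2 describes.

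A further point bears on any wider rule. Section 5.3.1 has Group A subjects rate loudness from 0 to 6, where 6 means the sound is too loud, for stimuli between 30 and 80 dB HL. This test is not listed for Group B. If a top rating counted as an event, the wider rule would itself create a source of events in one arm only.

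**The case against.** The strongest reply is that 8.2 should not be read alone. Table 2 marks adverse events at all five Group B post-activation visits, 8.1.1 is broad, and 10.2 and 10.3 are not limited to serious events. This stands. A reader might infer from 8.2 that over-stimulation is simply not recorded in Group B. The documents do not support that; they support only that 8.2 gives no clear route while the tables do.

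Second, the device of study includes functions related to the AI software for testing or programming. A reader might infer that an over-loud Group B MAP could never be a deficiency. That is one reading. The wording leaves it open whether ordinary programming software is covered, and section 4.2 does not settle it.

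Third, the Unscheduled Visit and Communication Documentation forms apply to both groups, and section 10.1 plans comparisons of both between models. This is real but partial capture, mainly relevant to trouble with a take-home MAP.

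Fourth, with commercially available processors and approved Custom Sound, limiting adverse event recording can be a proportionate choice. That is fair in principle, but a deliberate limit would have to be carried into the tables and 10.2 and 10.3, and it is not.

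Fifth, section 11.2 calls the risk very small, assigns it to all mapping, and describes mitigation similar to clinical practice. What it ties to the modified care plan is dissatisfaction and reduced performance, which the trial addresses in both arms. This stands against any claim about how often over-stimulation will occur or in which arm.

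**Conclusion.** The point holds as an internal contradiction over which safety events are collected, with an arm-unequal route under the narrower reading. Followed as written, 8.2 can lose non-serious over-stimulation in both arms or capture it only in Group A. Followed through the tables, the same event can be recorded in either arm.

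The conclusion rests on two readings: that transient uncomfortable loudness would ordinarily not be serious under 8.1.3, and that Group B programming involves no AI step, since none is listed.

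Its size cannot be expressed as an event count or a bias, because the protocol gives no rate beyond describing the risk as very small. It affects the safety data of all 35 to 50 planned subjects and leaves the primary and secondary endpoints untouched. The correction should be made, but it is a matter of reconciliation rather than a flaw in the trial's main comparison.

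Two further inferences should be resisted. One is that over-stimulation is the harm most likely to differ between the models; nothing in the documents ranks harms by arm. The other is that the trial will report an absence of device-related events; no such statement is planned in the protocol.

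**What to change.** Reconcile 8.2 with Tables 1 and 2 and with sections 10.2 and 10.3:

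- State one recording scope covering adverse events related to the device, programming or procedure, serious or not, applied identically in both arms and regardless of whether the MAP came from the AI or from Custom Sound. Use the existing Adverse Event form at the visits already marked.
- Clarify in the device deficiency definition whether the related functions include ordinary programming software, and apply that definition the same way in both groups.
- State that a top loudness rating given as a response within the Group A loudness-scaling test is not in itself an event, so that the wider scope does not create a Group A-only source.
- Leave expedited reporting of serious and unanticipated events as it is.

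This concerns data capture only and changes nothing about how MAPs are set or how over-stimulation is managed.

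The cost is a protocol wording change and a few more entries on an existing form. Section 4 excludes data entry and study forms from the timed appointment, so recording these events adds no minutes to the primary endpoint.
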